9.2 Analysis Datasets

This pilot study will provide preliminary effects sizes on all patient subjects and process evaluation data.

9.2.1 General Approach

This pilot study is a one-group pre-post pilot feasibility study design.

9.2.2 Adherence and Retention Analyses

Adherence to the protocol will be monitored on a monthly basis for both the cardiologists use of PA referral and counseling and patient subject use of Fitbit over 3 months and follow-up data collection. Completion/adherence data will be collected for all study endpoints.

9.2.2.1 Safety Review

The DSMB will review the occurrence of adverse and serious adverse events. This study may be temporarily suspended or prematurely terminated if there is sufficient reasonable cause as determined by the DSMB.

9.3 Sample Size

The purpose of this pilot study is to test our study protocol and obtain preliminary clinical efficacy data on patient outcomes. With a type 1 error of 5% and 80% power, a sample of 59 participants will allow us to detect a minimal clinically important difference (seen in adults with CVD) in the six-minute walk test of 25 meters.⁴⁵ (effect size =0.33) There is a potential for 20% attrition based on the PIs previous work. With a type 1 error of 5% and 80% power, this sample of 47 participants will allow us to detect an effect size of 0.41 (28 meters for the six-minute walk test, an increase of 9,710 in weekly step count, and an increase of 10% of the sample achieving recommended levels of PA) and will have 80% power to detect a small effect (R^2 of .09 to .11) associated with a predictor assuming up to 4 covariates which have a combined R^2 of .4 to .2

CONFIDENTIAL

This material is the property of the NYU School of Medicine and Langone Medical Center. Do not disclose or use except as authorized in writing by the study sponsor
Interventional Template Version: 11 January 2019

with change in average weekly PA. Given our timeline and weekly volume of patients we believe it is feasible to enroll a sample of 59 participants.

10 Source Documents and Access to Source Data/Documents

Access to study records will be limited to IRB-approved members of the study team. The investigator will permit study-related monitoring, audits, and inspections by the IRB, the sponsor, and University compliance and quality assurance groups of all study related documents (e.g. source documents, regulatory documents, data collection instruments, study data etc.). The investigator will ensure the capability for inspections of applicable study-related facilities (e.g. pharmacy, diagnostic laboratory, etc.).

Participation as an investigator in this study implies acceptance of potential inspection by government regulatory authorities and applicable University compliance and quality assurance offices.

11 Quality Assurance and Quality Control

QC procedures will be implemented beginning with the data entry system and data QC checks that will be run on the database will be generated.

Following written SOPs, the PI will verify that the clinical trial is conducted and data are generated, documented (recorded), and reported in compliance with the protocol and GCP.

12 Ethics/Protection of Human Subjects

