5.6 Total Number of Participants and Sites

This is a single site study conducted at the Preventive Cardiology Center (4F). All 59 subjects will be enrolled at this site.

Recruitment will end when approximately 59 subjects are enrolled. It is expected that approximately 59 participants will be enrolled in order to produce 47 evaluable subjects. We have anticipated approximately 20% attrition.

CONFIDENTIAL

This material is the property of the NYU School of Medicine and Langone Medical Center. Do not disclose or use except as authorized in writing by the study sponsor
Interventional Template Version: 11 January 2019

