9.1 Statistical and Analytical Plans (SAP)

Aim 1. Analysis will be performed using SAS 9.4. Surveys will be administered using the Research Electronic Data Capture (REDCap) system,⁴² a secure web-based tool licensed and supported by NYU. Standard descriptive statistics will be used to describe baseline sociodemographic and clinical characteristics. Mean scores and standard deviations as well as Cronbach's α will be calculated on questionnaires to confirm reliability of study instruments in our sample. Week 2 of the Fitbit Zip PA data will be used as baseline to assure the participant is accustomed to the device and to minimize the effect of reactivity, which can last approximately one week.⁴³ To calculate total minutes/week of PA from PAVS, the following standard calculation will be used:⁴⁴ light activity will be multiplied by 0 (light activity is not included in PA recommendations but is collected to acknowledge all attempts at PA and encourage increased intensity); moderate activity is multiplied by 1; vigorous activity is multiplied by 2 (one minute of vigorous activity being equal to two minutes of moderate activity). Paired t-tests will be used to assess changes in average PA from week 2 to three-month follow-up using PAVS and Fitbit Zip data. Using Fitabase software which allows for high resolution data, we will compare minutes of PA in three levels of intensity (light, moderate, and vigorous) as well as minutes spent in sedentary behavior. We will report the percentage of weeks each participant achieves the recommended levels of PA during the monitoring period and will assess weekly PA trends. We will compare improvements in PA by levels of protocol adoption by the HCP (e.g. 100% vs. 50% adoption). At 3 months we will compare mean minutes of moderate-to-vigorous PA between those who report achieving recommended levels of PA by the PAVS to those who do not. Paired t-tests will be used to assess changes in readiness to change number, the 6MWT, BMI, waist circumference, systolic and diastolic BP, lipids, and Framingham Heart Study Risk Score. To assess meaningful improvement in CRF, we will report the percent of participants who achieve a clinically important difference of 25 meters in the 6MWT.⁴⁵ Bivariate analyses will compare all CVD risk factors, as well as other potential confounders (e.g. age, sex, race/ethnicity, depressive symptoms, quality of life, comorbidities), between those who achieve PA recommendations and those who do not.

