Preliminary effect sizes of change in PA (step counts) will be generated following the Physical Activity Change Detection (PACD) approach.^{46,47} PACD is a framework for mining longitudinal PA data to detect and describe change over time. This method provides guidelines for defining time periods, detecting outliers, data smoothing, quantifying and describing change in PA patterns. Following data collection, longitudinal trends in PA will be examined descriptively and graphically to determine the optimal parameters for these analyses (e.g. window size- weekly or monthly; comparison type- baseline reference or rolling reference). An example of a possible structure is weeklong activity windows, and a static baseline reference. This would entail comparing average weekly step counts for each individual to their baseline (week 2) step counts. Significance of observed changes will be assessed, and effect sizes will be calculated to quantify the magnitude of change (e.g., Cohen's d). Plots of change over time will include error bars to reflect the precision of estimates. Benjamini-Hochberg method⁴⁸ will be used to control family-wise error rate for multiple comparisons. Lastly, exploratory linear regression analysis will be conducted to determine if change in average weekly PA is influenced by covariates. Change in physical activity between week 2 and 3 months will be the outcome variable, and the model will include up to 5 covariates, including week 2 physical activity to account for baseline levels of

CONFIDENTIAL

This material is the property of the NYU School of Medicine and Langone Medical Center. Do not disclose or use except as authorized in writing by the study sponsor
Interventional Template Version: 11 January 2019

activity. Up to 4 additional covariates will be selected from those identified in bivariate analyses of factors related to achieving physical activity goals.

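### Section 9.3: the effect sizes 0.33 (25 m, n=59) and 0.41 (28 m, n=47) for the six-minute walk test cannot share one sidedness or one SD of change

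*Combined protocol and SAP*

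**What the plan says.** Section 9.3 of the combined protocol and SAP makes two statements about the 6MWT.

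- For the full sample it begins "With a type 1 error of 5% and 80% power, a sample of 59 participants" and gives a detectable difference of 25 m, the plan's clinically important difference, with the label "effect size =0.33".
- After allowing for 20% attrition, at the same type 1 error and power, it says "this sample of 47 participants will allow us to detect an effect size of 0.41 (28 meters for the six-minute walk test". The same parenthesis attaches "an increase of 9,710 in weekly step count" to the 0.41 label.

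Section 5.6 matches these numbers: "It is expected that approximately 59 participants will be enrolled in order to produce 47 evaluable subjects". Section 9.1 fixes the test: "Paired t-tests will be used to assess changes in readiness to change number, the 6MWT, BMI, waist circumference", among other outcomes.

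No section states whether the tests are one- or two-sided, gives an SD for the change in 6MWT distance, or defines effect size for the 6MWT. Section 9.1 mentions Cohen's d only as an example, for step counts, and names no standardiser.

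**The concern.** For a paired test at fixed type 1 error and power, the detectable standardised change depends almost entirely on the square root of the sample size. Going from 59 to 47 should raise it by about 12%. The metres do rise by 12%, from 25 to 28, but the labels rise by 24%. Because metres and labels are linked by the SD, the paragraph is using two different SDs, two different sidedness conventions, or two different meanings of effect size.

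The 25 m difference is a main stated justification for 59 participants. As written, a reader cannot tell which SD or which sidedness supports the claim of 80% power, and on one combination of readings that claim fails.

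**Working it through.** **Inputs.** From Section 9.3: type 1 error 5%, power 80%, n=59 with 25 m and 0.33, n=47 with 28 m and 0.41. From Section 9.1: paired t-test. Sidedness and SD of change are not given, so both sidedness conventions were run. The attrition step is consistent: 59 × 0.8 = 47.2.

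**Detectable effect.** By normal approximation, d = (z for type 1 error + z for power)/√n, with √59 = 7.681 and √47 = 6.856.

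- One-sided: 1.6449 + 0.8416 = 2.4865, giving 0.324 and 0.363.
- Two-sided: 1.9600 + 0.8416 = 2.8016, giving 0.365 and 0.409.

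Solving the noncentral t distribution for 80% power gives slightly larger values.

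| Basis | n=59 | n=47 | Ratio |
|---|---|---|---|
| One-sided, t | 0.328 | 0.368 | 1.124 |
| One-sided, normal | 0.324 | 0.363 | 1.120 |
| Two-sided, t | 0.371 | 0.417 | 1.125 |
| Two-sided, normal | 0.365 | 0.409 | 1.120 |
| Plan's labels | 0.33 | 0.41 | 1.24 |

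The plan's 0.33 is reproduced one-sided only and its 0.41 two-sided only. No single row gives both.

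**Power and N at the stated labels** (t, with the normal approximation in brackets).

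| Label and n | Power one-sided | Power two-sided | N for 80% one-sided | N for 80% two-sided |
|---|---|---|---|---|
| 0.33, n=59 | 80.5% (81.3%) | 70.3% (71.7%) | 59 (57) | 75 (73) |
| 0.41, n=47 | 87.0% (87.8%) | 78.6% (80.3%) | 39 (37) | 49 (47) |

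**Rounding check on the ratio.** The labels could come from anything between 0.405/0.335 = 1.21 and 0.415/0.325 = 1.28. The required 1.12 to 1.13 lies outside that range. For the metres, 28/25 = 1.12 and 25 × √(59/47) = 28.01, so these agree.

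**Implied SD of change.** 25/0.33 = 75.8 m, with rounding range 24.5/0.335 = 73.1 to 25.5/0.325 = 78.5. 28/0.41 = 68.3 m, with rounding range 27.5/0.415 = 66.3 to 28.5/0.405 = 70.4. The ranges do not overlap.

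**SD that makes 25 m at n=59 exactly 80%.** Two-sided: 25/0.3709 = 67.4 m (t) or 25/0.3647 = 68.5 m (normal). One-sided: 25/0.3276 = 76.3 m (t). Each of these gives a detectable change of about 28 m at n=47, so the metres alone cannot identify the sidedness.

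**Consequence of the adverse combination.** If the SD is 75.8 m and the test is two-sided, power for 25 m is 70.3% at n=59 and 60.1% at n=47 (t).

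**Step count.** 9,710/0.41 = 23,683 steps per week as the implied SD. If the basis is one-sided, the detectable effect at n=47 is 0.3681, and 0.3681 × 23,683 = 8,718 steps.

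**The case against.** The strongest reply is that the labels need not be on the same scale. The 0.33 comes straight after the source cited for the 25 m difference, while 0.41 is introduced as what the sample can detect. If 0.33 used an SD measured at one time point and 0.41 used the SD of change, both could be correct. Since the variance of change is 2 × SD² × (1 − r), this needs a pre-post correlation r = 1 − 68.3²/(2 × 75.8²) = 0.59. The documents state no such correlation and define neither label, so this cannot be excluded. It does not rescue the paragraph: on that reading 0.33 is not the effect the planned paired test detects and should not be presented as if it were.

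It is also fair to say that this is a one-group pilot, that the metres agree with each other, that the plan already discloses 28 m for 47 participants, and that N also rests on Section 5.6's target of 47 evaluable subjects and on feasibility. All of this stands and limits the consequence.

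A reader might infer from the second decimals that one label was computed by t and the other by normal approximation. That is not supported. By t, the labels have 80.5% power one-sided and 78.6% two-sided; by normal approximation, 0.3237 and 0.4087 rounded up give 0.33 and 0.41. Either method accommodates both labels within ordinary planning tolerance, provided the sidedness switches.

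**Conclusion.** The point holds. As standardised mean changes for a paired test at one type 1 error and one power, 0.33 at n=59 and 0.41 at n=47 cannot share a sidedness or an SD of change. The label ratio is 1.24 (1.21 to 1.28 with rounding) where 1.12 to 1.13 is required. This rests only on figures in Section 9.3 and the test named in Section 9.1.

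Three stronger conclusions are tempting but are not supported.

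- A reader might assume two-sided testing and conclude that the study has 70% power and needs 75 participants. That requires both two-sided testing and 0.33 as the true standardised effect for 25 m. If instead the SD of change is about 67 to 68 m, 59 participants give 80% two-sided and 0.33 is simply the wrong label.
- A reader might conclude that both labels are wrong. Once the sidedness is fixed, essentially one has to change; the documents do not say which.
- A reader might quote one power figure for 25 m with 47 participants. Assuming that the stated 80% at n=59 holds gives about 70%, but crossing the two implied SDs with the two sidedness conventions gives 60.1% to 79.6% (t). No single value can be given without a sourced SD.

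This should be fixed, but it does not undermine the sample size or the planned analyses.

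**What to change.** Keep N=59. In Section 9.3:

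- State the sidedness of the 5% type 1 error.
- Define effect size as mean change divided by SD of change.
- Give one SD of 6MWT change, with its source.
- Correct whichever label does not fit. If two-sided, 0.33 becomes about 0.37 and 0.41 stays at 0.41 to 0.42, with an SD of about 67 to 68 m. If one-sided, 0.33 stays and 0.41 becomes about 0.37, with an SD of about 76 m; the 9,710-step figure tied to 0.41 must then be rechecked.
- If 0.33 was taken on another standardiser, say so and do not present it as the detectable effect of the paired test.
- If the sourced SD does not give 80% power for 25 m at n=59, restate the power or the detectable metres.

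The cost is rewording one paragraph. It needs no extra participants and no change to the analyses.

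### At n = 47 the regression power statement reproduces at its lower end (.09 with .4) but not its upper end: R² of .11 with covariate R² of .2 gives about 76% power, and 80% needs .12

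*Combined protocol and SAP*

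**What the plan says.** Section 9.3 plans for 59 enrolled, reduced to 47 by attrition: "There is a potential for 20% attrition based on the PIs previous work". For the 47 it sets the error rates once, "With a type 1 error of 5% and 80% power, this sample of 47 participants", and then makes several claims. The one at issue is "80% power to detect a small effect (R^2 of .09 to .11"), where the R² belongs to a single tested predictor. The other terms in the model enter the claim through a separate condition, "assuming up to 4 covariates which have a combined R^2 of .4 to .2".

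Section 9.1 describes the regression behind this claim. It is exploratory, the outcome is change in physical activity from week 2 to 3 months, and "the model will include up to 5 covariates, including week 2 physical activity". That is week 2 activity plus up to four others, which agrees with one tested predictor and up to four covariates in Section 9.3.

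Neither section names the test, states whether it is one- or two-sided, or says that the two ranges are to be read pairwise.

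**The concern.** The larger increment is set against the smaller covariate R², which is the right direction: the less variance the covariates explain, the larger the increment needed for a given power. If both ends come from one calculation at one sample size, both should give 80%. They do not.

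Little is at stake. Section 9.3 is the trial's only sample-size justification, and a power figure printed there should follow from the inputs printed beside it, not least because pilot figures may be carried into later planning. No endpoint, sample size or decision rule depends on this one.

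**Working it through.** **Inputs**
- n = 47, alpha = 5%, stated power 80% (Section 9.3).
- Increment in R² for the tested predictor, Δ: .09 to .11 (Section 9.3).
- Combined R² of up to 4 covariates, C: .4 to .2 (Section 9.3), paired in the order printed.
- Model size: 5 terms (Sections 9.1 and 9.3), so residual df = 47 − 5 − 1 = 41.
- Sidedness is not stated. I assume the usual F test of one added predictor, which is two-sided.

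**Formulas**
- f² = Δ / (1 − C − Δ)
- Noncentrality λ = n × f²
- Power = P(F′ > critical value), with F′ noncentral F on 1 and 41 df; the 5% critical value is 4.079.

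**Step 1: reproduce the plan's figure at the lower end (.09 with .4)**
- f² = .09 / (1 − .4 − .09) = .09/.51 = 0.176
- λ = 47 × 0.1765 = 8.29
- Power = 80.3%. The smallest n reaching 80% is 47, and the exact increment needed is .0894, which prints as .09. This end matches the plan, so the formula is very probably the one used.

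**Step 2: the upper end (.11 with .2)**
- f² = .11 / (1 − .2 − .11) = .11/.69 = 0.159
- λ = 47 × 0.1594 = 7.49
- Power = 76.2%, which is 80 − 76.2 = 3.8 points short.

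**Step 3: what 80% needs at C = .2**
- At fixed n and df, equal power requires equal f². Since .12/.68 = .09/.51 = 0.176, the partner of .09 with .4 is .12 with .2, also at 80.3%.
- The exact increment for 80% is .119.
- Keeping Δ = .11 would need n = 52.

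**Step 4: does another reading recover 80% at both ends?**

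| Reading | .09 with .4 | .11 with .2 |
|---|---|---|
| Noncentral F, two-sided (as above) | 80.3% | 76.2% |
| Normal approximation | 82.1% | 78.2% |
| One-sided test | 88.2% | 85.2% |
| λ = f² × (df + 2) | 76.7% | 72.5% |
| Random predictors | 74.5% | 70.3% |
| Fisher z | 73.4% | 69.2% |
| f² = Δ/(1 − C) | 73.7% | 69.9% |
| R² read as partial R² | 55.8% | 65.3% |
| n = 59 instead of 47 | 88.6% | 85.3% |

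None puts both ends within 2 points of 80%. Assuming fewer covariates (3 or none) moves the upper end only to 76.3% or 76.4%. Crossing the pairs is worse: .09 with .2 gives 66.4%, and .11 with .4 gives 88.7%.

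**Step 5: rounding**
- Δ = .1149, about the largest value that prints as .11, with C exactly .2: 78.3%.
- Δ = .1149 with C = .225, which prints as .2: 79.7%.
- C = .25, at the edge of what could print as .2: the increment needed is .112, which prints as .11.

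**The case against.** The best defence is rounding. The covariate R² is printed to one decimal and the increment to two, so a calculation run at a covariate R² somewhat above .2 could lead to a printed .11. Step 5 shows that this is possible, but only if the covariate R² lay well above .2 and the increment was rounded down as well; with C exactly .2, rounding of the increment alone reaches only 78.3%. Rounding may explain how the figure arose. It does not make the printed inputs deliver the printed power.

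A second defence is that the test is unspecified. A one-sided test would give more than 80% at both ends. It would not give the stated 80% at either, so it is not a natural reading, but it is a fair reason to ask that the test be named.

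Two stronger readings are tempting, and the documents do not support them:

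- A reader might infer that the word *small* is itself an error, since an f² of 0.16 to 0.18 is usually called medium. That rests on an outside convention. The plan sets no benchmark, never mentions f², and prints the R² values beside the word, so the reader can see what size is meant.
- A reader might infer that a null regression would be misread as excluding small effects. Nothing in the plan proposes this. Section 9.1 calls the regression exploratory, and Section 9.3 gives the aim as testing the protocol and obtaining preliminary efficacy data.

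The regression also does not set the sample size: Section 9.3 ties 59 to the six-minute walk test and 47 to attrition. Section 9.1's limit of five terms is consistent with Section 9.3 and is not a second error.

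**Conclusion.** The point holds as a minor arithmetic discrepancy. As printed, the .09/.4 end has 80.3% power at n = 47 and the .11/.2 end has 76.2%, a shortfall of about 4 points; the matching upper figure is .12 (exactly, .119).

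This assumes a two-sided F test for one added predictor, five model terms, alpha 5%, R² read as the increment, and the ranges paired in printed order. The first pair's close agreement with the plan supports those assumptions. The number of covariates hardly matters; the pairing and the sidedness do. Rounding of the covariate R² may account for part of the gap.

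The finding goes no further than that. It does not make the trial too small, does not affect the paired comparisons, and does not show that the plan would misinterpret a null result.

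**What to change.** In Section 9.3, do one of the following:

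- print the detectable range as .09 to .12 for covariate R² of .4 to .2; or
- keep .11 and report about 76% power at the .11/.2 end.

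In either case, state that the test is a two-sided F test of one added predictor at alpha 5%, and that the ranges are paired respectively. If the original calculation used a covariate R² other than .2, print that value instead.

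Optionally, replace the word *small* with the value itself (f² about 0.18). This is a matter of wording, not part of the error.

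The cost is one figure and one clause, slightly less favourable to the plan, with no change to the sample size, endpoints or analysis.

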12.1 Ethical Standard

The investigator will ensure that this study is conducted in full conformity with Regulations for the Protection of Human Subjects of Research codified in 45 CFR Part 46, 21 CFR Part 50, 21 CFR Part 56, and/or the ICH E6.

Institutional Review Board

The protocol, informed consent form(s), recruitment materials, and all participant materials will be submitted to the IRB for review and approval. Approval of both the protocol and the consent form must be obtained before any participant is enrolled. Any amendment to the protocol will require review and approval by the IRB before the changes are implemented to the study. All changes to the consent form will be IRB approved; a determination will be made regarding whether previously consented participants need to be re-consented.

CONFIDENTIAL

This material is the property of the NYU School of Medicine and Langone Medical Center. Do not disclose or use except as authorized in writing by the study sponsor
Interventional Template Version: 11 January 2019

